## Figures

Figure No.	Title
4.1.1	Forest Plot of Objective Response Rate as Determined by Independent Review Committee
4.2.1	Kaplan-Meier Estimates of Duration of Response as Determined by Independent Review Committee
4.2.2	Kaplan-Meier Estimates of Duration of Response as Reported by Investigator
4.2.3	Kaplan-Meier Estimates of Progression-Free Survival as Determined by Independent Review Committee
4.2.4	Kaplan-Meier Estimates of Progression-Free Survival as Reported by Investigator
4.2.5	Kaplan-Meier Estimates of Overall Survival
4.2.6	Waterfall Plot of Best Percentage Change in Disease Burden as Determined by Independent Review Committee
4.2.7	Waterfall Plot of Best Percentage Change in Disease Burden as Reported by Investigator
4.3.1	Kaplan-Meier Estimates of Duration of Response as Determined by Independent Review Committee – Censoring Crossover Participants
4.3.2	Kaplan-Meier Estimates of Duration of Response as Reported by Investigator – Censoring Crossover Participants
4.3.3	Kaplan-Meier Estimates of Progression-Free Survival as Determined by Independent Review Committee – Censoring Crossover Participants
4.3.4	Kaplan-Meier Estimates of Progression-Free Survival as Reported by Investigator – Censoring Crossover Participants
4.5.1	Kaplan-Meier Estimates of Time to Onset of Selected TEAEs of Special Interest
4.5.2	Kaplan-Meier Estimates of Longest Duration of Selected TEAEs of Special Interest
4.6.1	Line Graph of Mean Values Over Time for Selected Laboratory Values (Hemoglobin, Platelet Counts, Leukocytes, Neutrophils, and Lymphocytes)
4.6.2	Kaplan-Meier Estimates of Time to Onset of Selected Worsening Laboratory Events of Special Interest

## Listings

Listing No.	Title
2.1.1	Participant Enrollment and Disposition Status
2.1.2	Participant Inclusion and Exclusion Criteria Violations
2.2	Protocol Deviations
2.3	Analysis Population
2.4.1	Demographic and Baseline Characteristics
2.4.2	Disease History
2.4.3	Prior Systemic Therapy
2.4.4	Prior Radiation Treatment
2.4.5	Prior Surgery or Surgical Procedure
2.4.6	Prior Stem Cell Transplant
2.4.7	Medical History
2.4.8	Prior and Concomitant Medication
2.4.9	Tumor Markers
2.5.1	Study Drug Compliance

Listing No.	Title
2.5.2	Study Drug Administration
2.6.1	Best Overall Response, Duration of Response, and Progression-Free Survival per Independent Review Committee
2.6.2	Best Overall Response, Duration of Response, and Progression-Free Survival per Investigator
2.6.3	Overall Response Assessment by Visit per Independent Review Committee
2.6.4	Independent Review Committee Response Assessment: Target Lesions
2.6.5	Independent Review Committee Response Assessment: Non-Target Lesions
2.6.6	Independent Review Committee Response Assessment: New Lesions
2.6.7	Overall Response Assessment by Visit per Investigator
2.6.8	Investigator Response Assessment: Target Lesions
2.6.9	Investigator Response Assessment: Non-Target Lesions
2.6.10	Investigator Response Assessment: New Lesions
2.6.11	Deaths and Overall Survival
2.6.12	Bone Marrow Examination
██████	████████████████████
2.6.14	Best Overall Response, Duration of Response, and Progression-Free Survival per Independent Review Committee – Censoring Crossover Participants
2.6.15	Best Overall Response, Duration of Response, and Progression-Free Survival per Investigator – Censoring Crossover Participants
2.7.1	Adverse Events
2.7.2	Serious Adverse Events
2.7.3	Grade 3 and Higher Adverse Events
2.7.4	Treatment-Related Adverse Events
2.7.5	Fatal Adverse Events
2.7.6	Adverse Events Leading to Interruption, Reduction or Discontinuation of INCB050465
2.8.1	Clinical Laboratory Values - Hematology
2.8.2	Clinical Laboratory Values - Chemistry
2.8.3	Abnormal Clinical Laboratory Values - Hematology
2.8.4	Abnormal Clinical Laboratory Values - Chemistry
2.8.5	Potential Hy's Law Events
2.9.1	Vital Signs
2.9.2	Abnormal Vital Sign Values
2.9.3	Alert Vital Sign Values
2.10.1	12-Lead ECG Values
2.10.2	Abnormal 12-Lead ECG Values
2.10.3	Alert 12-Lead ECG Values

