
 Pneumonitis (Grade 1). 	
Step 1: Interrupt INCB050465 until the toxicity has resolved.
 
Step 2: Restart INCB050465 at next lower dose. Monitor as clinically indicated.

 Pneumonitis (Grade ≥ 2). 	Permanently discontinue INCB050465.

 Skin toxicity (eg, rash, pruritus, unless otherwise specified; Grade 2 and 3). 	
Step 1: Interrupt INCB050465 until the toxicity has resolved to \leq Grade 1.
 
Step 2: Restart INCB050465 at same dose. If assessed as related to INCB050465, restart at next lower dose.

 Exfoliative dermatitis (Grade 1). 	
Step 1: Interrupt INCB050465 until the toxicity has resolved.
 
Step 2: Restart INCB050465 at next lower dose. Monitor as clinically indicated.

 Exfoliative dermatitis (\geq Grade 2). 	Permanently discontinue INCB050465.

 Intestinal perforation (any grade). 	Permanently discontinue INCB050465.

 PJP infection. 	Interrupt INCB050465. Permanently discontinue INCB050465 if PJP infection is confirmed.

 CMV infection. 	Subjects with CMV viremia without associated clinical signs of CMV infection should be carefully monitored. Consider interrupting INCB050465 for subjects with CMV viremia and clinical signs of infection until the infection has resolved. Restart INCB050465 reduced by 1 dose level if approved by the medical monitor.

Table 3: Guidelines for Interruption and Restarting INCB050465 (Continued)

ADVERSE EVENT	ACTION TAKEN
• Varicella zoster infection.	Interrupt INCB050465. Restart INCB050465 only by approval of the medical monitor.
• Any Grade 1 or Grade 2 toxicity unless otherwise specified.	Continue INCB050465 and treat the toxicity; monitor as clinically indicated.
• Any Grade 3 toxicity, if clinically significant and not manageable by supportive care unless otherwise specified.	Step 1: Interrupt INCB050465 up to 14 days until the toxicity has resolved to \leq Grade 1. Step 2: Restart INCB050465 at same dose. If assessed as related to INCB050465, restart at next lower dose. If interrupted for > 14 days, contact the medical monitor for approval to restart INCB050465. Monitor as clinically indicated.

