^f Timed triplicate ECGs will be obtained during the Day 1 visit (predose) and Week 4 visit (predose and 1.5 hours [\pm 15 minutes] after receiving study treatment).

^g Required at baseline except for reasons provided in Section 7.6.2.

^h If disease is present in bone marrow at baseline, a bone marrow biopsy will be required to confirm CR or may be performed as clinically indicated. For subjects with splenic MZL without measurable disease (ie, only have histologically confirmed bone marrow infiltration), a bone marrow biopsy/examination must be performed when the number of lymphocytes in the blood normalize.

ⁱ *Pneumocystis jirovecii* pneumonia prophylaxis should be given while subjects are receiving study treatment and continue for at least 2 to 6 months after the last dose of study treatment.

^j May be conducted by clinic visit, telephone, or email.

Table 7: Schedule of Laboratory Assessments

Laboratory Tests ^a	Section	Screening	Treatment				EOT	Safety Follow-Up
		Day -28 to -1	Day 1 ^b	Every 4 Weeks Through Week 48 (± 3 Days)	Every 12 Weeks From Week 48 (± 1 Week)	Other		EOT + 30-35 Days
Serum chemistries	7.5.7.1	X	X ^c	X	X		X	X
Hematology ^d	7.5.7.1	X	X ^c	X	X	X ^e	X	X
Serology	7.5.7.3	X		X ^f	X ^f			
HIV testing	7.5.7.3.1	X ^g						
Serum pregnancy	7.5.7.2	X ^h					X	
Urine pregnancy	7.5.7.2					X ⁱ		
Tumor/bone marrow biopsy	7.8.5	X ^m				X ⁿ		

^a All laboratory assessments must be performed at a central laboratory, unless otherwise specified (see Section 7.5.7).

^b All laboratory assessments are to be performed before administration of study treatment on Day 1, unless otherwise specified.

^c If chemistry and/or hematology laboratory assessments occurred in the preceding 7 days, Day 1 assessments may be omitted.

^d Hematology will be collected every 2 weeks for the first 8 weeks.

^e Week 2 (Day 15) and Week 6 (Day 43) ± 3 days.

^f Samples for CMV DNA analysis only.

^g Optional for subjects enrolled in the United States.

^h Only for females of childbearing potential; negative serum pregnancy test must be obtained within 14 days before administration of study treatment. Screening test may be performed centrally or at the investigative site laboratory.

ⁱ Only for females of childbearing potential; if a urine pregnancy test is positive, then a serum pregnancy test should be performed. Urine pregnancy must be collected every 4 weeks until last dose of study treatment.

[REDACTED]

Table 8: Laboratory Tests: Required Analytes

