8. SAFETY MONITORING AND REPORTING

8.1. Adverse Events

8.1.1. Definitions

For the purposes of this Protocol, an adverse event (AE) is defined as any untoward medical occurrence associated with the use of a drug in humans, whether or not considered drug related, that occurs after a subject provides informed consent. Abnormal laboratory values or test results occurring after informed consent constitute AEs only if they induce clinical signs or symptoms, are considered clinically meaningful, require therapy (e.g., hematologic abnormality that requires transfusion), or require changes in the study drug(s).

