#### **9.3.2. Laboratory Value Summaries**

All test results and associated normal ranges from central laboratories will be reported in SI units. Any laboratory test results and associated normal ranges from local laboratories will be converted to SI units.

When there are multiple laboratory nonmissing values for a participant's particular test at a scheduled visit, central laboratory values have higher priority over local laboratory values. If a tie still exists, the laboratory value with the smallest laboratory sequence number will be used in by-visit summaries.

Numeric laboratory values will be summarized descriptively in SI units, and non-numeric test values will be tabulated when necessary. In addition, line graphs will be provided for ALT, AST, hemoglobin, platelet counts, leukocytes, neutrophils, and lymphocytes.

Shift tables will be presented showing change in CTCAE grade from baseline to worst grade postbaseline. Separate summaries for abnormally high and abnormally low laboratory values

will be provided when the laboratory parameter has both high and low grading criteria. The denominator for the percentage calculation will be the number of participants in the baseline category. The number of participants who experienced worsening of laboratory abnormalities will be summarized by maximum postbaseline severity.

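### CMV DNA is measured repeatedly on treatment, but no visible planned output names it, so DNA-detected CMV reactivation that is not filed as an adverse event may go unreported

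*SAP*

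**What the plan says.** **What is collected.** In Protocol Table 7 the serology row is marked at screening, at the 4-weekly visits through Week 48 and at the 12-weekly visits from then on. Footnote f limits the on-treatment samples: "Samples for CMV DNA analysis only". Table 8 lists CMV DNA under serology, and Protocol 7.5.7.3 sends serology to the central laboratory. The row is blank for Day 1, end of treatment and safety follow-up. The extra early visits ("Week 2 (Day 15) and Week 6 (Day 43) ± 3 days") are for hematology.

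**What becomes an adverse event.** Protocol 8.1.1 opens its rule with "Abnormal laboratory values or test results occurring after informed consent constitute AEs only if they induce clinical signs or symptoms". It then adds three more routes: a judgement that the finding is clinically meaningful, a need for therapy, or a change in study drug. Protocol 8.2 says that findings below this definition are not to be reported as adverse events. For CMV, Protocol Table 3 states: "Subjects with CMV viremia without associated clinical signs of CMV infection should be carefully monitored".

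**What will be reported.** SAP 9.2.2 includes CMV infection among the treatment-emergent adverse events of special interest, by maximum severity and with any-grade time to onset. The listings in Appendix A run from 2.8.1 to 2.8.5: hematology, "Clinical Laboratory Values - Chemistry", abnormal values of each, and potential Hy's law events. SAP 9.3.2 adds that "non-numeric test values will be tabulated when necessary".

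**The concern.** CMV infection is on the special-interest list in both documents, and Protocol 1.3 records one discontinuation for CMV colitis in Study INCB 50465-101. Of the infections on the Protocol 8.5 list (PJP, CMV, herpes simplex, varicella zoster), CMV is the only one with a scheduled on-treatment laboratory test. Yet the only planned summary specific to CMV depends on whether an investigator files an adverse event.

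The SAP treats another pair of special-interest events differently. Protocol 8.5 lists ALT and AST elevations. SAP 9.2.2 leaves them off the adverse event list, and SAP 9.3.4 analyses them from laboratory values instead. CMV, which also has a scheduled central laboratory measure, gets no such analysis.

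The two regimens differ only after Week 8, and the maintenance doses were chosen to reduce adverse events that lead to withdrawal. If signless viremia is not summarised, readers lose an objective view of CMV reactivation by regimen and dosing period.

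**Working it through.** The documents give no CMV rate, so there is no figure to reproduce. The check is a count of scheduled tests, a comparison of rules with outputs, and an illustration on assumed values.

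**1. Scheduled tests (Protocol Table 7).**
- Weeks 4, 8, ..., 48: 48 / 4 = 12 postbaseline tests.
- Weeks 60, 72, 84 and 96: 4 more, so 16 by Week 96 for a participant still on treatment.
- Ceiling for Cohort 2 through Week 48: 12 × 90 = 1,080 results, if all 90 stay on treatment. The real number will be lower. Median treatment in Study INCB 50465-101 was 122.5 days, and 122.5 / 28 = 4.4, so a participant treated for that long would have had 4 tests.

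**2. Planned outputs that name CMV DNA or serology.**

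| Place in SAP | Content | CMV DNA named? |
|---|---|---|
| 9.3.4 | ALT, AST, neutrophils | No |
| Tables 3.3.1.1 to 3.3.3.5 | Hematology, chemistry | No |
| Tables 3.3.6, 3.3.7; Figure 4.6.2 | Laboratory events of special interest (9.3.4) | No |
| Figure 4.6.1 | Five hematology parameters | No |
| Listings 2.8.1 to 2.8.5 | Hematology, chemistry, Hy's law | No |

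The 2.8 listing numbers have no gap. One listing row is redacted, between 2.6.12 and 2.6.14, but it sits among the efficacy listings.

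**3. Following one participant through the rules.** Take a participant with a first positive CMV DNA result at Week 16 and no clinical signs. Table 3 calls for monitoring. Suppose there is no therapy, no change in study drug and no judgement that the result is clinically meaningful. Then 8.1.1 does not make it an adverse event, and 8.2 says not to report it as one. This participant does not enter the SAP 9.2.2 count and appears in no output that names CMV DNA. The result follows from the rules and needs no assumed rate.

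**4. Illustration only.** Let v be the share of participants with CMV DNA detected and f the share of those reported as an adverse event. Both are assumptions. The difference between the DNA-detected rate and the part of it seen through adverse events is v × (1 − f). For N = 90, in percentage points:

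| v (participants) | f = 0 | f = 0.25 | f = 0.5 | f = 0.75 | f = 1 |
|---|---|---|---|---|---|
| 5% (4.5) | 5.0 | 3.75 | 2.5 | 1.25 | 0 |
| 10% (9) | 10.0 | 7.5 | 5.0 | 2.5 | 0 |
| 20% (18) | 20.0 | 15.0 | 10.0 | 5.0 | 0 |

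The table shows that the answer depends on f, which the documents do not give.

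**The case against.** The strongest reply is that nothing is miscounted. The special-interest event is CMV infection, not CMV DNA positivity, and Protocol Table 3 itself separates viremia without clinical signs from viremia with them. A reader might infer that the reported CMV infection rate will be understated. The documents do not support that: the count can be right for what it measures, and the one CMV event cited from Study INCB 50465-101 was clinical disease that adverse event reporting caught. This part of the objection stands.

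A reader might also infer that CMV DNA is taken at every treatment visit, or that the SAP rules out reporting it. Neither is so. Day 1 and Weeks 2 and 6 are not CMV DNA visits. SAP 9.3.1 and 9.3.2 promise by-visit summaries of numeric laboratory values, and the documents do not say whether CMV DNA is recorded as a number. Non-numeric results may be tabulated at discretion. Appendix A is a guideline, and some shells are in a separate document.

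The safety endpoint in both documents names chemistry and hematology values, not serology, so no stated analysis is missing or contradicted. That also stands, and it limits the point to an improvement.

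The general wording does not remove the gap, however. By-visit summaries show the distribution at each visit. They do not show how many participants ever turned positive, when, or how many of those had a CMV infection adverse event. Discretion to tabulate is not a commitment.

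**Conclusion.** The point holds as a reporting gap, and closing it is a cheap improvement. CMV DNA is a required, centrally measured and repeated test, no visible planned output names it, and the stated rules allow viremia handled as the Protocol describes to stay out of the CMV adverse event count. DNA-detected reactivation may go unreported by an unknown amount: zero if every positive result is filed as an adverse event, and all of it if none is.

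This rests on the visible text of Appendix A, on the redacted listing row not being a CMV output, and on the unseen shells adding none. The figures in the illustration are assumed and are not estimates for this trial. The matter concerns safety reporting only. It does not touch the primary endpoint, sample size or power.

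**What to change.** Add to SAP 9.3 and Appendix A:

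1. A listing of CMV DNA results by participant and visit.
2. A table by regimen and dosing period with the number (%) positive at baseline. Among baseline-negative participants with at least one postbaseline result, it should give the number (%) with a first positive result, defined by the central laboratory's reporting limit, and the time to that result.
3. A cross-tabulation of CMV DNA positivity against a CMV infection treatment-emergent adverse event.

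Three details need stating. Table 7 sets Week 2 at Day 15 and Week 6 at Day 43, so Week 8 falls on Day 57 (7 × 8 + 1), the day maintenance dosing starts in Protocol Table 4. The SAP should say to which dosing period that sample belongs. Participants who cross over after maintenance starts should follow SAP 5.2. Time to first positive is known only to within the 4- or 12-week test interval, and no sample is scheduled at end of treatment or safety follow-up; a footnote should say so.

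Keep these as laboratory outputs. A combined row for adverse event or DNA positivity does not belong in Table 3.2.26, which is tabulated by adverse event severity; a positive result that is not an adverse event has no such grade.

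The cost is one table, one cross-tabulation and one listing from data the Protocol already collects. The CMV picture may look less favourable.
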